6.3.4 Resumption of Normal Activities

Subjects will complete a visual analog scale (VAS) daily from Day 1 (baseline) until either the subject reports that all usual activities (prior to influenza onset) can be performed or Day 56, whichever comes first. The VAS scale ranges from 0 to 10, where 0 indicates subject is unable to perform usual activities at all, and 10 indicates subject is able to perform all usual activities fully)

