6.3.5 Health Resource Utilization

The following parameters for health resource utilization will be documented on an ongoing basis during the study:

- Hospital admission and discharge date
- ICU admission and discharge date
- Rehospitalization and reason for rehospitalization up to the last follow-up visit (Day 56 ± 7 days)

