10.5 Handling of Missing Data

Procedures for handling missing data will be defined in the Statistical Analysis Plan, and may include last observation carried forward or an interpolation method.

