## 2 STUDY DESIGN AND OBJECTIVES

### 2.1 Trial Design

This is a Phase 2b, multicenter, randomized, double-blind, controlled study comparing the efficacy and safety of 2 dose levels of VIS410 (2000 and 4000 mg) in combination with oseltamivir vs oseltamivir alone in hospitalized subjects with influenza A infection requiring oxygen support. Subjects will be randomly assigned at a ratio of 1:1:1 using a permuted block randomization method to receive VIS410 at a dose of 2000 mg (low dose) or 4000 mg (high dose) or placebo (0.9% sodium chloride), administered as a single IV infusion over 2 hours. Randomization will be stratified by presence or absence of positive pressure ventilation (PPV) at baseline to ensure an even distribution across treatment arms. All subjects will receive oseltamivir 75 mg twice daily (BID) for 5 days (total of 10 doses) as part of standard of care. Treatment with oseltamivir may be extended for up to 5 additional days (up to 20 doses of total therapy) if clinical symptoms warrant further treatment as assessed by the Investigator. Depending on standard of care, subjects may have started oseltamivir therapy prior to randomization. All subjects will also receive a pretreatment regimen of diphenhydramine 50 mg PO or IV plus either ibuprofen 400 mg PO or acetylsalicylic acid 320-325 mg PO approximately 60 minutes before infusion. Approximately 120 evaluable subjects (40/arm) with confirmed influenza A infection will be treated.

Study assessments are outlined in the Schedule of Assessments (copy in Appendix 16.2). Subjects discharged from the hospital prior to Day 14 will attend the applicable out subject follow-up visit(s) (e.g., Day 3, Day 5, Day 7, Day 14) per Table 1. The total study duration for each subject (screening through study exit) will be approximately 8 weeks (Day 56).

January 17, 2019

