## 2.2 Primary Hypothesis

The primary hypothesis for the study is that treatment with VIS410 + oseltamivir will lead to better clinical outcomes compared to oseltamivir alone.

The study is exploratory in nature and is not powered to demonstrate significant differences between treatment groups in primary or secondary outcome measures. The protocol intent is to collect sufficient information to identify the most appropriate candidate endpoints for subsequent Phase 3 study evaluation from among the primary and secondary endpoints described below. Statistical significance testing will therefore be used to assess the relative strength of evidence of the primary and secondary endpoints, to provide reasonable assurance that the endpoints chosen for a confirmatory Phase 3 trial will elucidate treatment differences between VIS410 plus oseltamivir versus oseltamivir alone.

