## 4 GENERAL ANALYSIS DEFINITION

### 4.1 General Considerations

All statistical analyses and summary information are to be generated according to this SAP. Any deviations from this SAP will be documented in the clinical study report (CSR).

These descriptive statistics will be presented for continuous parameters: the number of subjects used in the calculation (n), mean, standard deviation (SD), median, minimum, and maximum values. For PK parameters, the geometric mean and coefficient of variance (CV) will also be presented. All continuous summaries will display the minimum and maximum value with the same number of decimals collected in the data. The median, mean, geometric mean and CV will display 1 additional decimal, and the SD and SE will display 2 additional decimals. For categorical variables, frequencies and percentages will be reported. All percentages will be reported to 1 decimal; all p-values will be reported to 3 decimals.

All temperature measurements will be presented as degrees Celsius. Degrees in Fahrenheit will be converted with this formula:

$$T_C = (T_F - 32) * (5/9),$$

where  $T_C$  is a Celsius temperature and  $T_F$  is a Fahrenheit measurement.

Since this is a phase 2 study rigorous control over type 1 error will not be used; all statistical comparisons will be performed using 2-sided tests at the 0.05 significance level, unless specifically stated otherwise. All null hypotheses will be defined as no treatment difference. All p-values are presented for informational purposes only; there will not be any adjustments for multiple comparisons.

All analyses, summary tables, figures, and data listings will be generated with SAS version 9.4 or higher. Specialized PK software will be used for some PK analyses.

Baseline is defined as the latest non-missing measurement taken prior to study drug administration.

January 17, 2019

All summaries will be by actual visit, no visit windows for analysis will be defined. In general, summaries will be by treatment groups, and will include a combined VIS410 treatment group, in addition to the individual low dose (2000 mg) VIS410, high dose (4000 mg) VIS410, and Placebo treatment groups, unless specified differently. Summaries of disposition, other baseline data, and adverse events will also include an overall column.

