### **9.1 Primary Efficacy Analysis – Day 7 Ordinal Scale Status**

The ordinal scale outcomes will be measured daily from Day 1 (Baseline) through Day 14 using the seven-level hierarchical scale with the classifications presented in the table below. The clinical outcomes therein are ordered from the worst clinical outcome to the best clinical outcome in descending order. For each day, subjects will be classified by the worst clinical

January 17, 2019

outcome for which they qualify. The number and percentage of subjects in each treatment group with each classification will be summarized for each day from Day 1 through Day 14, inclusive. For subjects who die prior to Day 7, the score of 7 will be carried forward through Day 14. If a subject is missing an ordinal scale value but is bracketed by the same values on immediately preceding and subsequent days, the value of the missing day will be imputed to be the same as the immediately preceding and subsequent days. If a subject is missing baseline ordinal scale values from Day 1, baseline values will be set to the Day 2 score. If subjects are missing Day 1 and Day 2, the baseline value will not be imputed. No other data will be imputed.

Clinical Outcome	Score
Death	7
ICU stay with mechanical ventilation	6
ICU stay without mechanical ventilation	5
Non-ICU hospitalization with supplemental oxygen	4
Non-ICU hospitalization without supplemental oxygen	3
Discharge with partial resumption of normal activities	2
Discharge with full resumption of normal activities	1

For use in overall summary statistical presentations, the ordinal categories will be assigned decreasing integer scores, with death a score of 7 and discharge with full resumption of normal activities a score of 1. Frequencies of ordinal scores at each visit will be generated and evaluated by proportional odds ratio analysis, as implemented by logistic regression, including a test of the proportional odds assumption and generation of common odds ratios. For this analysis, the reference response category will be 1= Discharge with full resumption of normal activities with the remaining response categories in numeric sequence to worst (7=Death). Additional exploratory analyses may be conducted to obtain a more complete understanding of the relationship of treatment to the ordinal response.

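### A living subject's missing Day 7 score is left missing unless the Day 6 and Day 8 scores match, although other collected records would settle many of these scores, and no sensitivity analysis covers the rest.

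*SAP*

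**What the plan says.** SAP 9.1 has two rules that can supply a missing Day 7 score. A subject who dies before Day 7 keeps score 7 through Day 14. A missing day takes its neighbours' value if the day before and the day after carry the same score. A third rule sets a missing Day 1 to the Day 2 score and does not affect Day 7. The section then closes the list: "No other data will be imputed". SAP 4.2 likewise leaves missing data missing in general.

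MITT membership (SAP 5.1.3) requires dosing and confirmed influenza A, not a Day 7 score. The sensitivity analyses in SAP 9.1 concern ICU stays prolonged for reasons other than disease severity; none concerns missing scores. Protocol 10.5 left the method to the SAP, saying that it "may include last observation carried forward or an interpolation method".

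The protocol collects related information apart from the ordinal scale. Section 6.3.5 lists hospital admission and discharge dates and "ICU admission and discharge date". Section 6.3.3 records ventilation start and stop times. Sections 6.3.4 and 8.4 describe a daily VAS, kept in the subject's diary after discharge, which stops once all usual activities are possible.

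**The concern.** A subject scored 2 on Day 6 and 1 on Day 8, with no Day 7 entry, is known to be at home on both sides of the gap. The seven-level primary analysis still drops this subject, because the two neighbours differ.

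The bracketing rule works best for subjects whose status is stable and fails for those in transition. Discharge and recovery are the transitions the endpoint is meant to capture. Missingness could therefore depend on status, and if it also differs by arm, the odds ratio shifts. Each arm has about 40 subjects, so a handful of lost scores is visible in the estimate. The p-values are intended to guide the choice of Phase 3 endpoints (SAP 2.2).

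**Working it through.** The documents give no Day 7 distribution, effect size or missing rate, so there is no plan figure to reproduce. The study "is not powered to demonstrate significant differences between treatment groups in primary or secondary outcome measures". Inputs from SAP 2.1 and 4.1: 40 per arm, allocation 1:1:1 (pooled VIS410 versus placebo 80:40), two-sided 0.05. Everything else below is assumed and marked as such.

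**1. Which missing Day 7 scores are filled**

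| Situation | Result under SAP 9.1 |
|---|---|
| Death before Day 7 | 7 |
| Day 6 and Day 8 present and equal | filled |
| Day 6 and Day 8 present but different | missing |
| Day 6 or Day 8 also missing | missing |
| Alive when lost before Day 7 | missing |

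Suppose only Day 7 is missing and the chance of a score change from one day to the next is q (assumed, independent between days). The share filled is (1 − q)². For q = 0.10, 0.20 and 0.30 this is 0.81, 0.64 and 0.49.

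**2. Whether other records settle the level**

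| Distinction | Record | Settles it? |
|---|---|---|
| In hospital or discharged | admission and discharge dates | yes |
| ICU or not (5–6 v 3–4) | ICU dates | yes |
| Ventilated or not (6 v 5) | ventilation start and stop times | yes |
| Oxygen or not (4 v 3) | SpO2 three times daily until stable; an O2 Support listing and oxygen-cessation endpoints in the SAP | implied, not clearly documented |
| Full or partial resumption (1 v 2) | daily VAS | yes if the diary was kept; otherwise narrowed to 1 or 2 |
| Lost before Day 7 | none after loss | no |

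The SAP already works across forms. Section 9.2.7 takes all-cause mortality from four CRFs, and 9.2.5 treats the first VAS of 10 as resumption of usual activities.

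**3. Precision**

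The information on the log odds ratio (Whitehead) is V = n1·n2·(n1+n2) / [3(n1+n2+1)²] × (1 − Σp³), with SE = 1/√V. Assume scores 1 to 7 at 25/30/15/15/5/7/3%. Then Σp³ = 0.0499.

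- 40 v 40: V = 128,000/19,683 × 0.950 = 6.18, SE = 0.402.
- With 10% lost (36 v 36), SE = 0.425. With 20% lost (32 v 32), SE = 0.451.
- Odds ratio detectable with 80% power, exp(2.80 × SE): 3.09 with full data, 3.29 at 10% loss, 3.54 at 20% loss.
- 80 v 40: SE 0.347 with full data, 0.389 at 20% loss.

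The loss of precision is modest.

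**4. Bias with no true effect**

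All ratios here are odds of a worse score on VIS410 relative to placebo, so values below 1 favour VIS410. They come from proportional-odds fits after removing subjects with scores 1 or 2.

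Same assumed distribution as in step 3:

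- 20% of discharged subjects lost in both arms: 1.00.
- 20% lost on placebo, 10% on VIS410: 0.91.
- 10% lost on placebo, 20% on VIS410: 1.10.

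Second assumed distribution, 15/30/15/18/8/10/4%:

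- Expected placebo discharges are 0.45 × 40 = 18. Losing 4 from placebo only is 4/18 = 22% against 0%.
- A fit to expected counts gives 0.83, both at 40 v 40 and at 80 v 40. Repeated simulation runs gave medians of 0.81 to 0.85, against 0.99 to 1.03 with full data.
- Losing 4 from each arm returns it to about 1.00.
- In 400 simulated trials, the null rejection rate was 4.3% with full data, 8.3% with the one-arm loss and 5.5% with equal loss.

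For scale, ln 0.83 = −0.19, just under half of the SE of 0.40.

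**The case against.** The strongest reply is that little may be missing and that what is missing may be balanced. Inpatients are monitored daily, Day 7 is a scheduled outpatient visit for discharged subjects, and the trial is double-blind with no evident reason for loss to differ by arm. With equal loss the odds ratio barely moves. The trial is exploratory, and SAP 4.1 presents p-values for information only. The 2-then-1 subject would also count as discharged on both days of the modified five-level scale, so the bracketing rule would fill that gap if it is applied there. These points stand and limit the size of the problem.

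They do not remove it. The Day 7 visit has a window of ±1 day, the diary in Protocol 8.4 does not include the ordinal score, and neither document says how a discharged subject is scored between visits. Secondary endpoints get fuller treatment: viral load is analysed with and without carry-forward (SAP 9.2.8), and clinical-response criteria carry forward (SAP 9.2.3).

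A reader might infer four stronger things that the documents do not support:

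- That the analysis is complete-case apart from bracketing. Deaths before Day 7 are carried forward.
- That the existing records determine every missing level. Oxygen use and a diary VAS may not be available, and nothing exists after a subject is lost.
- That the primary result will be biased by the 0.81 to 0.85 amount. That is a one-arm extreme.
- That the SAP breaches Protocol 10.5. That section only names options.

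**Conclusion.** The point holds in a limited form. For a living subject without matching neighbours, a missing Day 7 score removes the subject from the primary model, and no planned analysis tests the effect. Much of the information needed for subjects still in the study is collected elsewhere.

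The practical size cannot be determined, because it depends on an unstated missing rate and on whether loss differs by arm. Under the assumed distributions it runs from no bias (equal loss), through roughly 10% on the odds ratio (20% against 10% of discharged subjects), to about 15 to 19% in the one-arm extreme. The case for changing the plan rests on possible bias and on the low cost, more than on the modest precision gain.

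**What to change.** Before unblinding, amend SAP 9.1 as follows.

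1. Derive a missing Day 7 score from hospital and ICU dates, ventilation times and, where recorded, oxygen records.
2. For discharged subjects, use the VAS: 10 on Day 7, or an earlier 10 after which the VAS stopped, counts as full resumption; below 10 counts as partial.
3. Add one sensitivity analysis, such as multiple imputation, for scores that remain missing, including those of subjects lost before Day 7.
4. Keep the worse of the two bracketing scores only as a further sensitivity option, since it is a debatable single imputation.
5. Report by arm how many Day 7 scores were observed, filled, derived and still missing.

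No new data collection is needed. The cost is SAP wording and some programming. The small downside is that the VAS stands in for the full/partial split in a few subjects, a link that the scale itself does not define.

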Approximately 120 evaluable subjects will be enrolled. The study is exploratory in nature, and is not powered to demonstrate significant differences between treatment groups in primary or secondary outcome measures. The protocol intent is to collect sufficient information to identify the most appropriate candidate endpoints for subsequent Phase 3 study evaluation from among the primary and secondary endpoints described below. Statistical significance testing will therefore be used to assess the relative strength of evidence of the primary and secondary endpoints, to provide reasonable assurance that the endpoints chosen for a confirmatory Phase 3 trial will elucidate treatment differences between VIS410 plus oseltamivir versus oseltamivir alone.

Efficacy

Efficacy analysis will have two complementary purposes in this Phase 2 study, both designed to aid in the optimal design of a confirmatory Phase 3 trial. First, primary and secondary endpoints will be analyzed for treatment group differences, to determine which endpoints might be most sensitive demonstration of treatment group differences using p-values as an indicator. Second, the relative contribution of the various efficacy endpoints to patient well-being and benefit will be assessed, as well as potential correlations of endpoints such as the influence of peak viral load or number of days on ventilator on the time to resumption of normal activities.

The ordinal scale outcomes will be measured daily from Day 1 (baseline) through Day 14, inclusive, using a seven-level hierarchical scale with the classifications ordered from the worst to the best clinical outcomes (see Section 10.6.1). For use in overall summary statistical presentations, the ordinal categories will be assigned decreasing integer scores, with death a score of 6 and discharge with full resumption of normal activities a score of 0. The primary outcome comparison of Ordinal Scale scores at Day 7 between treatment groups will be evaluated by proportional odds ratio analysis, as implemented by logistic regression, including a test of the proportional odds assumption. For this analysis, the response categories will be ordered from best (Discharge with full resumption of normal activities) to worst (Death). Additional exploratory analyses may be conducted to obtain a more complete understanding of the relationship of treatment to the ordinal response, including exact Mantel-Haenszel tests or partial proportional odds models.

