The area under the curve (AUC) over time for a given patient will be calculated as the sum of the maximum ordinal score for each day up through 7 and 14 days. An analysis of treatment group differences will be performed on these per-patient AUC values using analysis of variance, with treatment group and strata as fixed factors. A sensitivity analysis will be performed that excludes the category of death on study, to determine if death as an outcome skews the results; death as an outcome will also be analyzed as an independent secondary endpoint. A secondary analysis of treatment group effect on the difference in proportions of patients with the worst (death) versus the best outcome (discharge from hospital and resumption of normal activities) will also be performed. This analysis does not use scores for the ordinal outcome but does account for ordinality, and is therefore not dependent on the relationship of score to severity of outcome. An exploratory analysis will be performed through an exact categorical analysis of treatment group difference in the ordinal scale results using the worst outcome on a per-patient basis.

Additional ordinal scale outcome assessments will include comparison of total numbers of days at more severe scale values (death, time on ventilator, time in ICU) and proportions of patients with ordinal scale worsening post enrollment. Proportion outcomes will be analyzed by categorical data analysis methods, including Mantel-Haenszel chi-square tests adjusted for strata; additional exploratory subgroup analyses may also be performed, for example, based on various age categories. Time from onset of symptoms to study treatment and the number of doses of oseltamivir (Tamiflu) prior to VIS410 treatment for the current case of influenza may be included as covariates in the analyses.

Secondary and exploratory endpoints will be analyzed for descriptive purposes, with significance levels (p-values) provided to illustrate the strength of evidence for treatment effects, and to provide a basis for the choice of endpoints for further study in a confirmatory study. These analyses will also provide estimates for potentially powering additional efficacy endpoints, and to assist in hierarchical ordering of secondary endpoints to provide alpha-control in confirmatory studies and for labelling purposes.

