10.2 Randomization and Blinding

An IWRS will be used to allocate the randomized treatments to subjects with stratification by presence or absence of positive pressure ventilation (PPV) at baseline. Pharmacists must obtain the status of the subject relative to PPV at baseline via query, and this data must be input into the IWRS prior to randomization. The randomized treatment assignment will be transferred electronically for integration with the clinical study data at the appropriate time.

PPV includes any respiratory assistance using a mechanical ventilation device and can be either invasive or noninvasive ventilation. Invasive PPV includes intubation with endotracheal tube with mechanical ventilation (most common) or tracheostomy with mechanical ventilation. Noninvasive PPV includes use of facemask, nasal plugs, or nasal mask with mechanical ventilation. The devices are named according to the type of mechanical ventilation given continuous positive airway pressure (CPAP) or bi-level positive airway pressure (BiPAP).

Randomization will be used to avoid bias in the assignment of subjects to treatment, to increase the likelihood that known and unknown subject attributes (eg, demographic and baseline characteristics) are evenly balanced across treatment arms.

The maintenance of the study blind is critical for an unbiased assessment of the safety and efficacy of the study drug. All study staff that evaluate subjects and render decisions regarding subject care will remain blinded to the study treatment each subject receives.

The designated study site pharmacist or designee will remain unblinded. Also, unblinded clinical research associates will handle study drug accountability.

The study will be conducted in a double-blind manner. The CRO, site study personnel, and Visterra personnel will not be aware of which treatment (VIS410 or placebo) the subjects have been given. Subjects will not be aware of which treatment they have been administered.

Subjects will be randomized 1:1:1 to receive VIS410 2000 mg, VIS410 4000 mg, or placebo over a 2-hour infusion with pretreatment regimen of PO or IV diphenhydramine 50 mg plus either ibuprofen 400 mg PO or acetylsalicylic acid 320-325 mg PO approximately 60 minutes before IV infusion of VIS410/placebo.

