10.6.1 Day 7 Ordinal Scale Status

The ordinal scale outcomes will be measured daily from Day 1 (baseline) through Day 14 using the seven-level hierarchical scale with the classifications presented in Table 8. The clinical outcomes therein are ordered from the worst clinical outcome to the best clinical outcome in descending order. For each day, subjects will be classified by the worst clinical outcome for which they qualify.

The number and percentage of subjects in each treatment group with each classification will be summarized for each day from Day 1 through Day 14, inclusive.

Table 8. Hierarchical Seven-Level Ordinal Scale for Clinical Outcomes

Clinical Parameter
Death
ICU stay with mechanical ventilation
ICU stay without mechanical ventilation
Non-ICU hospitalization with supplemental oxygen
Non-ICU hospitalization without supplemental oxygen
Discharge with partial resumption of normal activities
Discharge with full resumption of normal activities

Note: Clinical outcomes listed from worst clinical outcome to best clinical outcome in descending order.

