## 9.2 Other Analyses

### 9.2.1 Secondary Endpoints Assessing Ordinal Scale Status

The area under the curve (AUC) over time for a given subject will be calculated (using the linear trapezoidal rule) as the sum of the maximum ordinal score for each day up through Day 7 and Day 14. An analysis of treatment group differences will be performed on these per-subject AUC values using analysis of variance, with treatment group and randomization strata as fixed factors. A sensitivity analysis will be performed that excludes the category of death on study, to determine if death as an outcome skews the results; death as an outcome will also be analyzed as an independent secondary endpoint using all available death information.

A secondary analysis of treatment group effect on the difference in proportions of subjects with the worst (death) versus the best outcome (discharge from hospital and resumption of normal activities) will also be performed. This analysis does not use scores for the ordinal outcome but does account for ordinality and is therefore not dependent on the relationship of score to severity of outcome. P-values will be based on logistic regression treatment comparisons of best vs. worst vs. other categories adjusting for randomization strata.

An exploratory analysis will be performed through an exact categorical analysis of treatment group differences in the ordinal scale results using the worst outcome across all assessments on a per-subject basis.

Additional ordinal scale outcome assessments will include comparison of total numbers of days up to and including Day 14 at more severe scale values (death, time on ventilator, time in ICU) and proportions of subjects with ordinal scale worsening post enrollment.

Using the modified ordinal scale described in Table 2, frequency analyses by visit, AUC analyses (up to Day 7 and up to Day 14) and best versus worst versus other analyses will also be generated.

Proportion outcomes will be analyzed by categorical data analysis methods, including logistic regression adjusted for strata. Additional exploratory subgroup analyses may also be performed, for example, based on various age categories or other subgroup variables. Time from onset of symptoms to study treatment and the number of doses of oseltamivir (Tamiflu) prior to VIS410 treatment for the current case of influenza may be included as covariates in the analyses.

Clinical Outcome	Score
Death	5
ICU stay with mechanical ventilation	4

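### The primary Day 7 proportional-odds model names no PPV term, although PPV is the only randomisation stratum and other analyses of the same scale adjust for it

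*SAP*

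**What the plan says.** **The primary model.** SAP 9.1 gives "Frequencies of ordinal scores at each visit will be generated and evaluated by proportional odds ratio analysis, as implemented by logistic regression", with a test of the proportional odds assumption and common odds ratios. No covariate or stratum is listed. The Protocol Synopsis (Statistical Methods, Efficacy) is equally bare: "The primary outcome comparison of Ordinal Scale scores at Day 7 between treatment groups will be evaluated by proportional odds ratio analysis". Protocol 10.6.1 is descriptive only: "The number and percentage of subjects in each treatment group with each classification will be summarized for each day".

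**The stratum.** SAP 2.1: "Randomization will be stratified by presence or absence of positive pressure ventilation (PPV) at baseline". No other factor is named. Protocol 10.2 requires the pharmacist to obtain PPV status, and "this data must be input into the IWRS prior to randomization".

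**Other analyses of the same scale.** For the ordinal AUC the Synopsis specifies "using analysis of variance, with treatment group and strata as fixed factors", and SAP 9.2.1 "using analysis of variance, with treatment group and randomization strata as fixed factors". SAP 9.2.1 also adjusts the best/worst/other logistic regression and the proportion outcomes for strata.

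**Use of the p-values.** The Synopsis says the endpoints are analysed "to determine which endpoints might be most sensitive demonstration of treatment group differences using p-values as an indicator". SAP 2.2 likewise uses significance testing to support the choice of Phase 3 endpoints.

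**The concern.** Stratifying the randomisation on PPV implies that PPV is expected to matter. The scale supports this. PPV covers any assistance from a mechanical ventilation device (Protocol 10.2), mechanical ventilation in the ICU is the second-worst level, and Protocol 6.3.9 classes a ventilated patient on the hospital floor as a mechanical ventilation patient. A PPV subject can therefore start near the bad end of the outcome scale.

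Leaving a balanced prognostic stratum out of a logistic model does not inflate type I error. It makes the test conservative and pulls the odds ratio towards 1, because the model then estimates a marginal quantity. Read literally, the plan would rank an unadjusted primary analysis against stratum-adjusted AUC, best/worst/other and proportion analyses of the same data. Part of any difference in p-values could then come from the models and not from the endpoints. The SAP also leaves open which common odds ratio, marginal or conditional, is to be reported.

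**Working it through.** **Does another section close the gap?** No. SAP 4.3 lists PPV only as an optional subgroup. The end of SAP 9.1 brings in severity covariates only as exploratory follow-up if the ICU-bed sensitivity analyses disagree. SAP 16.1 (changes to protocol-specified analyses) is silent. The table shells are a separate document, to be completed after the SAP text (SAP 16.7).

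**Is the primary alone?** No. The by-day models fall under the same SAP 9.1 sentence. The five-level by-visit and exact worst-outcome analyses (9.2.1), the Cox model (9.2.2), the Kaplan-Meier comparisons (9.2.3, 9.2.4), the FluPRO tests (9.2.6) and the viral-load ANOVA (9.2.8) also name no PPV term.

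**Size of the effect.** The current plan states no power or effect size, so there is no figure to reproduce.

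*From the documents:* about 120 subjects, 1:1:1, permuted blocks within PPV stratum, two-sided 0.05, pooled VIS410 (80) or one dose (40) against placebo (40).

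*Assumed:* block size 6; placebo Day 7 distribution without PPV, scores 1 to 7, of 15/35/15/20/6/6/3%; PPV share 5% to 35%; PPV odds ratio (OR) for a worse score 1 to 20; conditional treatment OR 2.5.

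*Models compared*, with T for treatment, b for the treatment log OR and g for the PPV log OR:
- unadjusted: logit P(score ≤ k) = a_k + b·T
- adjusted: logit P(score ≤ k) = a_k + b·T − g·PPV

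Both were fitted to the same 12,000 simulated trials per setting with Wald tests. The Monte Carlo standard error is at most √(0.25/12,000) = 0.46 points.

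*Power points gained by adding PPV, pooled 80 vs 40:*

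| PPV OR | PPV 5% | 10% | 20% | 35% |
|---|---|---|---|---|
| 2 | 0.7 | 0.9 | 1.1 | 1.8 |
| 3 | 0.8 | 1.9 | 2.5 | 3.6 |
| 5 | 1.7 | 3.3 | 5.1 | 7.4 |
| 10 | 3.1 | 5.5 | 10.3 | 15.8 |

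- At PPV OR 1 the difference is 0.2 to 0.3 points, so there is no power cost. At OR 20, an extreme, the gain is 4.9 to 25.8.
- At PPV 20% and OR 5, power goes from 69.7% to 74.8%.
- One dose vs placebo (40 vs 40), PPV 5/20/35%: 0.5/1.9/2.3 points at PPV OR 2, 1.0/3.3/4.5 at OR 3, 2.0/6.5/8.9 at OR 5.
- Unadjusted type I error: 4.5% to 5.4% at PPV OR 1 to 3, 3.3% to 5.1% at 5, 1.4% to 4.6% at 10 to 20. Adjusted: 4.7% to 5.7% throughout.
- Median p at PPV 20%, unadjusted vs adjusted: 0.010 vs 0.009 at PPV OR 2, 0.012 vs 0.009 at 3, 0.016 vs 0.009 at 5.
- Three assumed non-proportional PPV effects: gain 0.2 to 7.1 points, adjusted type I error 5.0% to 5.7%.

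**A second simulation**, with placebo distribution 20/38/12/17/6/5/2% and 4,000 trials per setting, agrees. At treatment OR 2.5, pooled power rises from 72.0% to 73.9% (PPV 10%, OR 3) and from 67.7% to 74.9% (PPV 20%, OR 6). For 40 vs 40 the rises are 60.5% to 62.1% and 54.2% to 62.6%.

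**Marginal against conditional odds ratio, by hand.** Take PPV 20%, PPV OR 5, treatment OR 2.5 and the cut between scores 2 and 3.
- Placebo: without PPV, P(score ≤ 2) = 0.50, odds 1; with PPV, odds 1/5, P = 0.167. Mixture 0.8 × 0.50 + 0.2 × 0.167 = 0.433, odds 0.765.
- VIS410: odds 2.5 gives P = 0.714; odds 0.5 gives P = 0.333. Mixture 0.8 × 0.714 + 0.2 × 0.333 = 0.638, odds 1.763.
- Ratio 1.763 / 0.765 = 2.31 at this cut. The common odds ratio fitted over all cuts is 2.33.

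**The case against.** The SAP is silent; it does not say that the model is unadjusted, and the programmed model might include PPV. The trial is exploratory and unpowered (SAP 2.2) and its p-values are informational (SAP 4.1). Stratified randomisation already limits imbalance. Every input that drives the size of the loss is assumed, and entry requires only some oxygen support (Protocol 5.2.1), so PPV may be rare: at PPV 5% and PPV OR 2 to 3 the pooled gain is under 1 point. Most efficacy analyses name no PPV term, so adjusting only the Day 7 and by-day models would leave the primary ranked against unadjusted Cox, Kaplan-Meier, FluPRO and viral-load results. The adjusted Wald test can also run slightly above 5%.

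Much of this stands, and it limits the severity. The gains at PPV OR 10 to 20 should carry no weight in the judgement. The adjusted test's upper figure of 5.7% is a real but small excess. None of it supplies the missing term. SAP 4.1 requires analyses to follow the SAP, and the shells come after it, so the text has to decide between two defensible models that report different odds ratios. The exploratory status does not remove the point either, because ranking endpoints by p-value is the stated use of the testing.

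**Conclusion.** The concern holds and should be fixed. The primary Day 7 model is incompletely specified, and its literal reading omits the only randomisation stratum while three other analyses of the same scale adjust for strata. The unadjusted test would be valid and its estimate unbiased for the marginal odds ratio; the cost is sensitivity. For PPV odds ratios of 2 to 5 and PPV shares of 5% to 35%, that cost is about 1 to 7 power points for the pooled comparison and about 0.5 to 9 for a single dose, at a treatment odds ratio of 2.5. It is negligible if PPV is rare or weakly prognostic. The textual gap is certain; its size rests on assumptions, although other placebo distributions (30/40/10/13/3/2/2% and 8/20/15/30/10/10/7%) give similar pooled gains at PPV 20%: 2.2 to 2.9 points at PPV OR 3 and 5.2 to 5.3 at OR 5.

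**What to change.** In SAP 9.1:

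1. State the Day 7 model and the by-day models as treatment plus PPV randomisation stratum, as entered in the IWRS.
2. Say that the reported common odds ratio is conditional on the stratum, and keep the unadjusted (marginal) model as a sensitivity analysis.
3. Report the proportional-odds test for the treatment term, so that a departure due to PPV is not read as one due to treatment.
4. Set a minimum PPV count, fixed before unblinding, below which the unadjusted model is used. A count rule is cleaner than waiting to see whether the model converges. At PPV 5% the stratum would hold 120 × 0.05 = 6 subjects; even there, non-convergence was at most 1.0% for PPV OR up to 10.

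To make the endpoint ranking like for like, also state for each remaining efficacy analysis whether it includes the stratum.

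The cost is SAP wording and one model term. PPV status is recorded before randomisation, so nothing is re-derived and no site query is needed. The estimand becomes conditional, and no power is lost if PPV turns out not to be prognostic.
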